8.1.4 Analysis of secondary objectives

- 1) To examine the association of baseline demographic characteristics with HIV incidence and prevalence in a household-based representative sample of men and women before and after completion of the MC ASI. Within each cohort, logistic regression will be used to assess association of baseline demographic characteristics with HIV prevalence. Poisson, survival and logistic regression will be used as appropriate to assess associations with seroincidence and baseline demographics. Combined analysis of predictors of seroprevalence and seroincidence using both cohorts will assess effect modifiers associated with cohort (e.g. time) using test for interaction with time. Sample weights will be used in all analyses.
- 2) To determine the prevalence of circumcision among men before and after completion of MC ASI. Population-based circumcision prevalence rates will be computed using appropriate sample weights.
- 3) To estimate HIV prevalence rates among men and women before and after completion of the national male circumcision ASI. Population-based age and gender HIV prevalence rates will be computed using appropriate sample weights.
- 4) To describe sexual risk behavior in a household-based representative sample of men and women before and after completion of the MC ASI. This analysis will be conducted in both HIV-infected and HIV-uninfected participants. Sexual risk behaviors compared between the enrollment pre and post- MC ASI surveys will include the proportion of men and women reporting any unprotected sex and proportion reporting more than one partner. Logistic regression will be used to assess differences in proportions between the baseline cohorts, adjusted for baseline demographic factors, HIV status, and circumcision status (men).

In the two longer longitudinal cohorts of younger HIV-uninfected men (25-34 yrs) and women (18-24 yrs), logistic regression will be used to compare change in behavior from baseline to follow-up. Factors predicting increase and decrease in risk behaviors will be assessed.

- 5) To describe the proportion of HIV-infected men and women in a household-based representative sample of men with undetectable viral loads before and after completion of MC ASI. Logistic regression will be used to assess differences in proportions of male participants with undetectable viral load.
- 6) To measure the proportion of HIV-infected men and women in a household-based representative sample of men and women who report engagement in HIV care and ART use before and after completion of the MC ASI. Logistic regression

will be used to compare any engagement in care and any ART use in the HIV infected persons identified in the household surveys.

- 7) To describe the CD4 count distribution in a nationally representative sample of HIV-infected men and women ages 18-49. Standard survey sampling approaches using sampling weights will be used to estimate proportions and 95% confidence limits.
- 8) To estimate the proportion of HIV-infected men and women ages 18-49 who have a CD4 count <350 cells/mm³ and who report no current ART use. Standard survey sampling approaches using sampling weights will be used to estimate proportions and 95% confidence limits.
- 9) To describe the viral load distribution in a nationally representative sample of HIV-infected men and women ages 18-49. Standard survey sampling approaches using sampling weights will be used to estimate proportions and 95% confidence limits.

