HIV testing coverage is relatively low, with 17% and 36% of men and women 15-49 years reporting having ever been tested and receiving test results [CSO, 2008.] In contrast, projections of ART coverage, based upon modeling of national health systems data, indicate widespread coverage. In 2009, approximately 45,748 HIV-infected adults were estimated to be on ART, accounting for 93% of the population projected to have a CD4 count less than 200 and 59% of the population modeled to have a CD4 count less than 350 [UNAIDS, 2010]. A more recent estimate from the 2011 MOH Quarterly Service Coverage Report places ART coverage using a CD4 threshold of 350 at 79.5% (MOH QSCR, 2011). National goals aim for 85% coverage of all ART-eligible adults (i.e. CD4 count below 350) by 2014 [NERCHA, 2009].

HIV prevention efforts in Swaziland have primarily focused on behavioral change strategies such as delaying sexual debut, encouraging partner reduction and/or fidelity to one partner, and consistent and correct condom use at every sexual encounter. Unfortunately, the success in reducing HIV incidence from these initiatives has fallen far short of the goals established by the Swazi government and the President's Emergency Plan for AIDS Relief (PEPFAR) strategies.

Lack of male circumcision (MC) has been identified as one of the key drivers of the Swazi HIV epidemic [Swaziland, 2009]. Only 8% of men reported being circumcised during the 2007 Demographic and Health Survey (DHS) [CSO, 2008]. Based on strong scientific evidence that male circumcision is efficacious at reducing HIV acquisition among men, the Swazi government developed an HIV prevention strategy with a focus on the rapid scale-up of male circumcision services nationwide.

Male Circumcision for HIV prevention

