Swaziland's National MC Task Force created an initial MC strategy to circumcise 80% of 15-24 year old males within 5 years, and implementation of this strategy began in 2008. In the interim, the Government of Kenya launched a national month-long MC campaign, and 36,000 boys and men were circumcised in 30 working days. Based upon Kenya's success, PEPFAR's MC Technical Working Group suggested to Swaziland that an acceleration of their strategy from 5 years to 1 year might be feasible, and PEPFAR mobilized resources to assist.

Modeling conducted by the Future's Group in support of the accelerated approach projected that circumcising 80% of 15-49 year old men in one year could avert 88,000 new HIV infections by 2025, and that 1 HIV infection could be prevented for every 3-4 circumcisions performed. Annual HIV incidence under this accelerated scenario could be reduced by approximately 70% by 2025. Consequent HIV care and treatment cost savings could total over US\$650 million over the same time period. Thus, in early 2010, the GKOS outlined an unprecedented national MC program—the MC Accelerated Saturation Initiative (ASI)—to provide voluntary medical MC to 80% of HIV-uninfected males aged 15-49 years by the end of 2011. There are approximately 240,000 15-49 year old males in the country; 92% are estimated to be uncircumcised, 80% are estimated to be HIV-negative. This equates to approximately 176,000 males that are uncircumcised and HIV-negative, 80% of which (the ASI target) equals approximately 140,000 males. Depending on the number of HIV-infected males who also seek MC after counseling regarding the lack of HIV prevention benefit, as many as 175,000 boys and men are anticipated to voluntarily receive MC services.

Program Description

The GKOS plans to launch the MC ASI in January 2011. Services delivered will include the following activities in addition to voluntary medical MC:

- information and education for both men and women on MC as an HIV prevention strategy;
- pre-operative provider-initiated HIV testing and counseling (PITC);
- individualized and partner HIV risk reduction counseling;
- syndromic screening and treatment for STIs;
- promotion and provision of male and female condoms; and
- either the offer of voluntary HIV testing and counseling (VCT) for sex partners of surgical candidates or couples HIV testing and counseling for sex partners who accompany surgical candidates to MC facilities.

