- Risk compensation refers to the phenomenon whereby individuals may engage in increased risk behavior due to the perception that measures taken to safeguard their health confer greater protection than is actually the case [Cassell et al., 2006]. There was little evidence of pre- to post-surgical risk compensation among men in the three MC clinical trials [Auvert et al., 2005; Bailey et al., 2007; Gray et al., 2007]. However, this lack of risk compensation among RCT participants may not reflect what may be observed in non-research implementation settings. It is also important to note that for participants in these clinical trials, the efficacy of MC for HIV prevention was yet to be determined with certainty. As mentioned previously, MC RCT participants experienced a frequency and intensity of counseling and follow-up that was different from what will occur in non-research settings. Though modeling studies suggest that risk compensation limited to men undergoing MC would not appreciably reduce the protection from HIV acquisition conferred by circumcision, these same studies suggest a potential attenuation of benefit if risk compensation were to occur among women and uncircumcised men in communities undergoing MC scale-up [Hallett et al., 2008]. Thus, risk compensation outside of research settings needs to be measured and characterized among both circumcised and uncircumcised men as well as women.

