From the sample of 5823 men in the pre-MC-ASI cohort (Cohort Aa), we expect 25% of the men to be aged 25-34, a sample of 1456. From the sample of 6,165 men in the post-ASI cohort (Cohort A2), we expect 25% of the men to be aged 25-34, a sample of 1,541. If we compare the seroincidence in the 26-34 year old men 6 months prior to MC ASI to the seroincidence in the 18 months period (24-42 months following the end of the pre-MC-ASI cohort), we would have ~80% power to detect a 50% reduction in HIV seroincidence, assuming a pre-MC-ASI seroincidence of 5.0 per 100 person years, after accounting for lost to follow-up of 12% per year, and a design effect of 1.25 in each cohort

Primary Objective #2b

To estimate HIV incidence rates in the highest risk age subsets of women ages 18-24 in the household-based, nationally representative sample for an additional 6-18 months after the MC ASI completion (Cohort B).

From the sample of 7524 women in the post-ASI cohort (Cohort A2), we expect 29% of the women to be aged 18-24, a sample of approximately 2183. If we compare the seroincidence in the 6 months prior to MC ASI to the seroincidence at 24-42 months following MC ASI, we would have ~80% power to detect a 40% reduction assuming a seroincidence of 6.0 per 100 person years, after accounting for lost to follow-up of 10% per year, and a design effect of 1.25 in each cohort

Primary Objective #3

To estimate HIV incidence of circumcised compared to uncircumcised men in a household-based representative sample of men post- MC ASI (Cohort A2).

The 6165 men in the post-MC ASI cohort (A2) gives 71% power to detect a 55% decrease in the HIV incidence rate ratio between circumcised and uncircumcised men, assuming 80% of the men are circumcised and 20% are uncircumcised (i.e. a ratio of 4:1) and the seroincidence rate in the uncircumcised men is 2.5 per 100 person years, 12% loss to follow-up. If 2/3 of the men are circumcised, the power is increased to 83%. As the comparison will be within the cohort, no adjustment for design effect is assumed.

As the primary objectives capture the most important scientific objectives of importance, power consideration are only given for these objectives.

Secondary Objectives #8, and #9

- 8) To describe the concurrent CD4 count and viral load distributions in a nationally representative sample of HIV-infected men and women ages 18-49, in the context

of ART use.

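### The pre/post comparison of men's risk behaviour adjusts for circumcision status, which the campaign itself changes, so its coefficient is not the population change

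*Protocol*

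**What the plan says.** Secondary objective 4a (section 3.2) is to describe risk behaviour in representative household samples of men and women before and after the campaign. Section 8.1.4, item 4, names the quantities compared: "the proportion of men and women reporting any unprotected sex and proportion reporting more than one partner". It then fixes the model, a logistic regression for the difference between the two surveys, "adjusted for baseline demographic factors, HIV status, and circumcision status (men". The two samples are drawn independently (sections 4.0 and 5.1), so baseline in this sentence means enrolment into each survey. For the second survey that is after the campaign. For this objective the section names no model without circumcision status and no survey-by-circumcision interaction.

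On coverage, section 2.1 says "Only 8% of men reported being circumcised during the 2007 Demographic and Health Survey (DHS" and gives the campaign's aim as "to provide voluntary medical MC to 80% of HIV-uninfected males aged 15-49 years by the end of 2011". Section 7.2 also considers lower coverage: "If 2/3 of the men are circumcised, the power is increased to 83".

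On purpose, section 2.2 says "risk compensation outside of research settings needs to be measured and characterized among both circumcised and uncircumcised men as well as women". Section 9.3.2 lists knowledge of risk compensation under large programmes as a societal benefit. Section 4.4 wants to see whether changes in incidence coincide with behaviour change, including change brought about by the campaign.

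**The concern.** A covariate belongs in a before/after comparison when it differs between the samples for reasons unrelated to what happened in between. Age structure is such a covariate. Circumcision status is not, because changing it is the purpose of the campaign. With it in the model, the period coefficient compares uncircumcised men before with uncircumcised men after, and circumcised with circumcised, and averages the two contrasts. A man who becomes circumcised and then takes more risk moves from one group to the other, and much of his change passes into the circumcision coefficient.

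That coefficient cannot stand in for risk compensation, because men choose circumcision. Section 8.1.7 itself says riskier men may be more inclined to seek it. The same selection also distorts the period coefficient: it changes who is left in each circumcision group in the second survey even if no man changes his behaviour.

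At stake is a misleading answer on one stated reason for the study: no change, or a decline, reported for men whose behaviour as a population rose or stayed level.

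**Working it through.** The protocol gives no effect size, power or behaviour rate for this objective, so there is no figure to reproduce. The check fits the stated model to expected counts.

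**Inputs from the protocol.** Coverage before is 8% and after is 80%, with 2/3 as the protocol's own alternative. Men enrolled number 5,823 and 6,165. Of men surveyed, 77% are HIV-uninfected and 99% of those agree to enrol. Men surveyed: 5,823/(0.77 × 0.99) ≈ 7,639 and 6,165/(0.77 × 0.99) ≈ 8,087.

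**Assumed.** Behaviour is reported by 30% of men at the lower level and 40% at the higher level. Post-campaign coverages of 40% and 20% are further assumptions.

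**Models.** Unadjusted: logit(p) = a + b·post. As written, demographics and HIV status aside: logit(p) = a + b·post + c·circumcised. The odds ratio is exp(b).

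**A. All circumcised men, before and after, at 40%; uncircumcised at 30%.**
- Before: 0.92 × 0.30 + 0.08 × 0.40 = 0.308. After: 0.20 × 0.30 + 0.80 × 0.40 = 0.380.
- Population odds ratio: (0.380/0.620)/(0.308/0.692) = 1.38.
- Within each circumcision group nothing changes, so the adjusted odds ratio is 1.00.

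**B. Only newly circumcised men move to 40%.**
- Before: 0.300 in both groups. After: uncircumcised 0.300; circumcised (0.08 × 0.30 + 0.72 × 0.40)/0.80 = 0.390; overall 0.372.
- Population odds ratio: (0.372/0.628)/(0.300/0.700) = 1.38.
- Within groups the odds ratios are 1.00 (uncircumcised) and (0.390/0.610)/(0.300/0.700) = 1.49 (circumcised).
- The adjusted estimate is a weighted average of these, here 1.13. On the log scale 0.122/0.324 = 38% is kept and 62% lost.

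**C. A rise shared by all men, 30% to 40%.** Unadjusted and adjusted odds ratios are both 1.56, so nothing is lost.

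**D. Selection only, no man changes.** Assume 30% of men are high-risk, behaviour is 50% in high-risk and 20% in other men, and overall coverage after is 80%.
- Overall, both periods: 0.30 × 0.50 + 0.70 × 0.20 = 0.29; true odds ratio 1.00.
- With 90% uptake in high-risk men, uptake in the others is (0.80 − 0.27)/0.70 = 75.7%. After the campaign, behaviour is 24.5% in uncircumcised and 30.1% in circumcised men. Adjusted odds ratio 0.87.
- With 95% uptake, the two figures are 22.3% and 30.7%. Adjusted odds ratio 0.81.

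**Other coverages, 30% against 40%:**

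| Coverage after | A: unadjusted → adjusted | B: unadjusted → adjusted |
|---|---|---|
| 80% | 1.38 → 1.00 | 1.38 → 1.13 |
| 2/3 | 1.30 → 1.00 | 1.30 → 1.09 |
| 40% | 1.16 → 1.00 | 1.16 → 1.06 |
| 20% | 1.06 → 1.00 | 1.06 → 1.03 |

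**Other behaviour rates.** Under B at 80% coverage, 20% to 30% gives 1.50 → 1.17, 40% to 50% gives 1.34 → 1.12, and 30% to 35% gives 1.18 → 1.06. In the last case z falls from 4.8 to 1.3, before any design effect.

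**The case against.** The strongest reply is that the protocol also wants behaviour within circumcision status. Section 2.2 names circumcised men, uncircumcised men and women, and section 2.5 is interested in how behaviour in each group changes. A model containing circumcision status speaks to that question. Women's models have no such term, and a rise common to all men survives (case C). This stands, but as a reason for a second analysis. A single averaged coefficient gives neither the change within each status nor the population change.

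Second, section 8.1.7 describes matching on propensity scores and marginal structural models, which deal with self-selection more directly. The protocol says only that the first will be explored and the second may be useful, so neither replaces the stated comparison. The Cohort B behaviour analysis begins at Month 36 and has no pre-campaign arm.

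Third, weighted crude proportions would probably be tabulated, and companion models may be in an analysis plan not shown here. That is fair, but the covariate is fixed in the protocol, and the comparison stated there is the adjusted one.

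Fourth, the 80% target applies to HIV-uninfected males, this analysis includes HIV-infected men, and section 4.3 allows that coverage may differ. Lower coverage shrinks the population change as well as its loss, as the table shows.

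A reader might infer that the model removes all risk compensation in men. The protocol does not support that. Complete removal requires that men circumcised before the campaign already behave like the newly circumcised.

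**Conclusion.** The point holds for the men's pre/post behaviour comparison. Circumcision status is a consequence of the campaign and does not belong in a model meant to show the population change. The loss is complete if all circumcised men behave at the higher level. It is about 62% to 67% on the log-odds scale at 2/3 to 80% coverage if only the newly circumcised do, and zero for a rise shared by all men. Selection alone can produce an apparent decline, to 0.87 or 0.81 under the stated inputs. All behaviour rates, the high-risk share and its uptake are assumptions; only the coverages of 8%, 2/3 and 80% come from the protocol.

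This is a secondary, descriptive objective without a power calculation, and section 7.1 already declines to attribute behaviour trends to the campaign alone. It should be corrected, but a reader should not carry it over to the primary incidence comparison, which section 8.1.3 bases on a Poisson model with a pre/post covariate.

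**What to change.** In section 8.1.4, item 4, make the men's pre/post comparison without circumcision status, adjusted for demographics, the main analysis. Add a separate analysis of behaviour by circumcision status with a period-by-circumcision interaction. Label it as change within status, subject to self-selection, and not as the population change. HIV status in the second survey is also measured after the campaign, so if it stays in the model the reason should be given.

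The cost is a sentence or two of text. No new data and no further participants are needed.

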by revising the current policy for ARV initiation from < 200 CD4 cells to < 350 CD4 cells. ARV treatment scale-up may also impact population-level HIV incidence as HIV infected people may decrease behaviors that transmit HIV once they are aware of their HIV status [Rietmeijer et al., 1996; Gibson et al., 1999; Cleary et al., 1991] and ART-induced viral suppression reduces the risk of HIV transmission to sex partners [Granich et al., 2010; Wagner and Blower 2010, Quinn et al., 2000; Attia et al., 2009; Donnell et al., 2010; Sullivan et al., 2009; Reynolds et al., 2009; Cohen et al., 2011]. In fact, mathematical models indicate that the 50, 767 Swazi adults provided with free ARV treatment between 2006-2009 by the ECTIP prevented 10,770 new adults infections, assuming a one-year treatment retention of approximately 85%. This is approximately 18% of infections that would have occurred in the absence of the program. Furthermore, the MC ASI will result in more individuals identified as HIV-positive who will be linked to HIV care and treatment services. The anticipated changes in risk behavior and viral suppression may also affect transmissibility and reduce HIV incidence, but this is unlikely to occur within the timeframe of this study.

In summary, Swaziland is taking a lead role in implementing a combination of prevention interventions at an unprecedented pace. It is vital to describe changes in the rate of new HIV infections resulting from implementation of these interventions. The study described in this protocol seeks to document changes in HIV incidence and examine factors that may contribute to this change so that other countries and programs can develop and implement HIV prevention strategies that will lead to documented reductions in HIV incidence.

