4.4 Limitations to the study designs

The accelerated nature of the MC ASI prevents the use of evaluation designs that allow causal inference to a particular intervention such as serial rollout of different interventions or of establishment of one intervention in certain geographic areas and not others. In addition, given the overwhelming evidence of the efficacy of MC at preventing HIV acquisition among men, it would be unethical to have a true comparison group, even if that group were wait-listed for services. Instead, multiple evaluation designs and data collection on other factors that could influence HIV incidence besides an increase in MC prevalence will be used in an attempt to distinguish the effect of each of these variables on HIV incidence. For example, data on HIV-related sexual risk behaviors will be collected to determine if changes HIV incidence coincide with change in risk behaviors, resulting from the MC ASI or other ongoing HIV prevention interventions. Additionally, data on prevalence of persons on ART and proportion of persons with undetectable viral load will be collected to assist in understanding the potential effect of expanding care and treatment services on changes in HIV incidence. Cohort effects are a major threat to validity due to power reductions or bias from loss to follow-up and repeated measures (i.e. repeated counseling and interview sessions with staff reduces HIV acquisition risk among cohort participants over time). The two short term cohorts, with their one-time 6 or 12 month follow up will minimize cohort effects. The hybrid approach with addition of a longer term cohort with multiple follow-up observations will allow comparison of measurements from the different methodologies.

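### The before/after comparison of sexual risk behaviour is worded as one model pooled over HIV status, so it can dilute, and under larger opposite changes mask, the change in the HIV-uninfected people whose incidence it is meant to explain

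*Protocol*

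**What the plan says.** Section 8.1.4, item 4, fixes three things for the behaviour comparison between the two enrolment surveys.

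- **Population:** "This analysis will be conducted in both HIV-infected and HIV-uninfected participants".
- **Endpoints:** "the proportion of men and women reporting any unprotected sex and proportion reporting more than one partner".
- **Model:** logistic regression on the survey difference, "adjusted for baseline demographic factors, HIV status, and circumcision status (men").

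No interaction between survey and HIV status is named. Item 1 of the same section does plan one for predictors of prevalence and incidence: it "will assess effect modifiers associated with cohort (e.g. time) using test for interaction with time".

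Elsewhere the protocol says what the behaviour data are for. Section 4.4: "data on HIV-related sexual risk behaviors will be collected to determine if changes HIV incidence coincide with change in risk behaviors". Section 2.2: "risk compensation outside of research settings needs to be measured and characterized among both circumcised and uncircumcised men as well as women". Section 2.3 notes that "HIV infected people may decrease behaviors that transmit HIV once they are aware of their HIV status".

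**The concern.** HIV status is constant within each HIV group, so it can act as a covariate only if the groups are analysed together. With main effects alone, the model then returns one before/after OR per endpoint and takes the change to be the same in both groups.

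The protocol gives reasons why it may not be. Section 2.2 raises possible risk compensation as circumcision is scaled up. Section 2.3 raises possible risk reduction after diagnosis, and Section 2.2 foresees as many as 34,000 men newly diagnosed through the programme. These would push in opposite directions.

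The incidence cohorts contain only HIV-uninfected people (Section 5.3.2). To ask whether incidence and behaviour moved together, as Section 4.4 intends, one needs the uninfected people's behaviour change. No other planned analysis supplies it before and after the campaign. Cohort B is uninfected, but it is enrolled at Month 36 and limited to men aged 25-34 and women aged 18-24, so it has no pre-campaign measurement.

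**Working it through.** The protocol states no effect size, power or behaviour level for this objective (Section 7.2 confines power to the primary objectives), so there is no figure of its own to reproduce.

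**Inputs from Section 7.2**
- HIV-uninfected share: 77% of men, 65% of women.
- Enrolled in A1 and A2: 5,823 and 6,165 men; 7,106 and 7,524 women. Agreement to enrol: 99%.
- Design effect 1.25. It is stated for HIV; using it for behaviour is an assumption.
- The counts are taken as stated. Separately, the men's household factor does not follow from its own terms: 1/(0.92 × 0.77 × 0.99 × 0.90 × 0.95) = 1.67, printed as 2.11.

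**Assumed:** 40% report the behaviour at baseline in both HIV groups; changes as tabulated; two-sided 5% test.

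**Numbers surveyed**
- Uninfected = enrolled/0.99: men 5,882 and 6,227; women 7,178 and 7,600.
- All = uninfected/share: men 7,639 and 8,087; women 11,043 and 11,692.

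**ORs within each group, +3 points uninfected and -5 infected**
- Uninfected: (0.43/0.57)/(0.40/0.60) = 1.13, log 0.124.
- Infected: (0.35/0.65)/(0.40/0.60) = 0.81, log -0.214.

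**Pooled OR.** The main-effects model gives roughly the share-weighted mean of the two log ORs.
- Women: 0.65 × 0.124 - 0.35 × 0.214 = 0.006, OR 1.01.
- Men: 0.77 × 0.124 - 0.23 × 0.214 = 0.046, OR 1.05.

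Fitting the model (intercept, survey, HIV status) to expected counts, with variance multiplied by 1.25, gives the following pooled ORs and 95% intervals:

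| Change, uninfected/infected | OR in uninfected | Pooled OR, women | Pooled OR, men |
|---|---|---|---|
| +3/-3 | 1.13 | 1.04 (0.98-1.10) | 1.07 (1.00-1.15) |
| +3/-5 | 1.13 | 1.01 (0.95-1.07) | 1.05 (0.98-1.13) |
| +5/-5 | 1.23 | 1.06 (1.00-1.13) | 1.12 (1.04-1.20) |
| +3/-10 | 1.13 | 0.94 (0.88-0.99) | 1.00 (0.93-1.07) |

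The women's interval at +5/-5 starts at 1.003, so it just excludes 1.

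**Point of full cancellation.** The fall in the infected must equal the rise in the uninfected times the ratio of shares: 0.65/0.35 = 1.9 in women, 0.77/0.23 = 3.3 in men.

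**What the uninfected alone would show for +3 points**
- Women: SE = √[1.25 × (1/(7,178 × 0.40 × 0.60) + 1/(7,600 × 0.43 × 0.57))] = 0.037; z = 0.124/0.037 = 3.3; power about 91%.
- Men: same formula with 5,882 and 6,227, SE 0.041, z = 3.0, power about 85%.

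Baselines of 15%, 30% and 50% give the same pattern.

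**The case against.** Five points can be made for the plan as written.

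1. **The wording may allow separate analyses.** Conducting the analysis in both groups could mean in each group. The covariate list favours pooling but does not say that one OR is the only output. This is an ambiguity, and the covariate points one way.

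2. **A reader might infer that the protocol expects opposite changes. It does not.** Section 2.2 treats risk compensation as a possibility to be measured and reports little evidence of it in the three trials. Section 2.3 does say "The anticipated changes in risk behavior and viral suppression may also affect transmissibility and reduce HIV incidence", but the sentence ends by calling this unlikely within the study's timeframe, whether that means the changes or their effect. The case rests on changes that may differ.

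3. **A reader might infer that the pooled result would be significant in the wrong direction.** That needs a case such as +3/-10 in women. There the interval is 0.883-0.994 with design effect 1.25, but 0.873-1.005 with the DEFT of 1.32 that Section 7.2 also states (variance factor 1.32² = 1.74). The 34,000 new diagnoses are men, and no comparable figure is given for women. The documents do not support this as a headline. The +3/-10 case in men also sits at the cancellation ratio, so its OR of 1.00 is built in.

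4. **The objective is descriptive.** An all-adult estimate answers a legitimate question and is not an error. This stands, and is why the pooled figure can be kept.

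5. **Interaction terms and subgroup reporting belong in the analysis plan, and Section 8.1.6 already calls for confounder control.** Here the protocol itself fixes population, model and covariates, so the point concerns what is stated. Section 8.1.6 covers analyses of incidence; it does not supply a before/after behaviour contrast in uninfected people.

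**Conclusion.** The point holds in a limited form. As worded, item 4 yields a before/after OR averaged over HIV status, while the comparison with incidence needs the change in HIV-uninfected people. If the two groups change differently, the pooled figure is diluted. At +3/-5 points from 40%, it is 1.01 in women and 1.05 in men against 1.13 in the uninfected, a rise that the uninfected alone would detect with about 91% and 85% power. Near-complete masking is plausible in women under moderate opposite changes; in men it takes a fall more than three times the rise. With equal-sized changes of 5 points, the pooled model still shows the rise in both sexes, though reduced.

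All behaviour levels and changes are assumed, and the design effect is borrowed from HIV status. If both groups change alike, the pooled estimate is sound and the more precise. This is a cheap improvement to a secondary analysis that helps interpret the primary result; the primary incidence comparison itself is unaffected.

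**What to change.** In Section 8.1.4, item 4, state that the before/after change in each behaviour will be estimated by sex in HIV-uninfected participants, and that this is the estimate to read beside the incidence change. Report HIV-infected participants separately, or fit one model with a survey-by-HIV-status interaction and report both ORs. The pooled all-adult estimate may remain, labelled as a description of the population.

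No new data are needed: anyone refusing the rapid test is reclassified as refusing the study (Section 6.1.2), so survey participants have been tested. The cost is two estimates per sex. For the uninfected, intervals widen by about √(1/0.65) = 1.24 times in women and √(1/0.77) = 1.14 times in men. For the infected the factors are larger, √(1/0.35) = 1.69 and √(1/0.23) = 2.09.
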